## Statistical Power and Statistical Analysis

**Statistical power:** For Aim 1, primary endpoint, with an n=75 and 50 completers, we will have >80% chance of detecting a difference in the rate of BMD AP lumbar spine increase of 0.024g/cm^2/y at a 2-sided  $p=0.05$  level. This compares favorably with the rate of BMD AP spine increase of 0.036 g/cm^2/y in a study by Baum *et al.* administering GH for 18 months to hypopituitary subjects with GH deficiency. This was calculated with software developed by co-investigator [REDACTED] for sample size for random slopes models, available in Matlab [REDACTED]. The variance covariance matrix of the random effects,  $\Psi$ , and residual variance,  $\sigma^2$ , were estimated from longitudinal data from Baum *et al.* that had originally been analyzed by [REDACTED]. The variance of the intercept was 0.024, slope 0.000211, covariance 0.00199 and residual variance,  $\sigma^2$ , 0.00092 and an exponential drop-out rate of 0.36/yr, which is greater than we expect. The program uses the fact that the variance covariance matrix for the fixed effects of the model are:  $\mathbf{V(B)} = \{\mathbf{X}'[\sigma^2] + \mathbf{Z\Psi Z}'\}^{-1}\mathbf{X}$ . One incorporates drop outs by replacing  $\mathbf{X}'[\sigma^2] + \mathbf{Z\Psi Z}'\}^{-1}\mathbf{X}$  by a weighted sum for different follow-up times with weights equal to the follow-up probability -- a special case of the general model described in Pinheiro and Bates. For Aim 2, primary endpoint, with 50 completers we can detect 0.81 x SD of the difference in bone marrow fat content over a year; For secondary endpoints: for trabecular thickness (TbTh) and cortical thickness (CoTh), based on our preliminary data in obese men receiving placebo for 6 months in which the standard deviation (SD) of the change in TbTh was 0.0047mm and of CoTh was 0.0015mm, we will be able to detect an annual increase of 0.008mm and 0.012mm, respectively; for FEA we will have a power of 80% at a two-sided  $p=0.05$  significance level, if the true rate of difference in estimated failure load between the treatments is 316 units, based on an assumption that the SD is 570 units, as derived from Boutroy *et al.* With 50 completers, we will have an 80% power at a 2-sided  $p=0.05$  level to see a difference in PINP of 38.6 ng/ml, total abdominal fat of 50.8 cm^2, lean mass of 1.2 kg, vitamin D of 0.025 ng/ml, hsCRP of 0.025 mg/l, and apoB of 18.6 mg/dl per year. These were calculated from our preliminary data administering GH to obese subjects for 6 months. The power for the mediation analyses (see below) depends on the effect size of the treatment on BMD and on the correlation of the secondary endpoint on BMD. We derived a formula using the delta method. With at least 40 subjects we will have an 80% chance of achieving significance at a two-sided  $p=0.05$  level if the effect size is 2 units and the correlation is 0.5. For the 6-month withdrawal period, we will have adequate power to test whether the BMD remains significantly different from placebo at 24 months. We will have 80% power to detect a difference of 0.04 g/cm^2 assuming that there are at least 43 patients still in the study at 18 months (we expect 50).

**Data analysis plan:** We will pool data from men and women using a random slopes model; we will consider a model where each patient has a random slope and intercept. The mean intercept and slope may be different for men and women and in each treatment group. The primary analysis is a pooled analysis of treatment effect across gender with weights equaling the frequency of men and women in the sample. A secondary analysis will test for the significance of the treatment-gender interaction on the rate of change of BMD and all other endpoints. For all analyses, an intent-to-treat analysis will be performed. We plan to apply the guidelines developed by the National Research Council regarding missing data. Our primary analysis, the random slopes model, assumes that data is missing at random. We also will conduct two sensitivity analyses. The first assumes that the missing data is a function of the unobserved random effect and the second tests the assumptions in this model under other missingness mechanisms. We will also determine which of the secondary endpoints appears to mediate the treatment effect on an endpoint, such as BMD, microarchitectural parameters, and bone marrow fat by examining the effect of treatment on the potential mediator and of the potential mediator on the endpoint; examples of this will include whether Pref-1 mediates the effects of GH on bone marrow fat or strength, and whether bone marrow fat, body composition variables, inflammatory markers, lipids or vitamin D mediate the effects of GH on bone strength. The effect on one endpoint by a potential mediator is the product of the two effects. The Sobel test will test whether this effect is zero. As there are no known moderators of GH treatment in this population and the population has been purposely selected for osteopenia, we will not control for covariates other than gender in our primary analysis. We will perform exploratory analyses to answer the following: 1. Among an osteopenic population are there covariates

(such as family history, smoking, alcohol, exercise, free testosterone or estradiol) that predict problems such as anomalies in bone microarchitecture and predicted strength? 2. Are these factors moderators of the treatment effect of GH? Both of these analyses will use stepwise variable selection using a random effects model as above. 3. Is the effect of GH on BMD mediated by IGF1? We will perform a mediation analysis using a random effects model with final GH dose and a final GH dose time interaction in the treated group.

**Timeline:** Screening, enrollment, and study visits will occur from year 1 through year 5. Data management will occur in years 1-5, and analyses and manuscript preparation will be performed in years 4-5.

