- Fasting glucose, HbA1c, IGF-1, TSH, creatinine, SGPT, urine pregnancy test, HCT, Ghrelin
- DXA scan to evaluate for osteopenia and body composition
- Measurement of bone age for males 18 or 19 years old

Study Visits:

1. Baseline: (n=75: 38 healthy obese women and 37 healthy obese men)

The baseline visit will occur within 8 weeks after the screening visit. The following assessments will be made during the baseline visit days and will occur within a 30-day period.

- Assessment of potential factors affecting BMD: family history of osteoporosis, alcohol, free testosterone, estradiol, exercise (Paffenbarger Physical Activity Questionnaire and Modified Activity Questionnaire (MAQ)), Calcium & Vitamin D Intake (Calcium & Vitamin D Frequency Questionnaire), and food diary log
- Waist circumference, weight, and BMI
- 2-hour GHRH-arginine GH stimulation testing

Partners Human Subjects Research Application Form Version Date: June 1, 2005

- CT
- DXA scan (only if baseline occurs more than 6 weeks after screening visit)
- Xtreme CT
- Head x-ray if subject reports possibility of metal in face or head
- MRI/MRS
- Blood drawn to determine levels of hormones and other chemicals
- Oral glucose tolerance test (OGTT)
- Functional Strength Test

2. Follow-up visits:

The following assessments will be made during the 6 week, 3 month, 4.5 month, 6 month, 9 month, 12 month, 15 month, 18 month and 24 month visits. The 3 week, 9 week, and 4 month visits will be performed during a \pm 2 week interval around the indicated return time to allow for potential scheduling conflicts. The 6 month, 9 month, 12 month, 15 month, 18 month and 24 month visits will be performed during a \pm 1 month interval around the indicated return time. Subjects who drop out or are discontinued from the study after participating for at least 9 months will be asked to come in for a final study visit that will be identical to the 18-month study visit. The follow-up visits involve:

- Medical history, physical examination, weight, waist and hip. Return menses (for women), growth hormone dosing records, and all study medication vials.
- DXA scan (12 month, 18 month, and 24 month visits)
- CT scan (18 month visit)
- Low-dose CT for body composition only (6 month visit)*
- Xtreme CT scan (12 month, 18 month, and 24 month visits)
- MRI/MRS (6 month visit* and 18 month visit)

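### The claim of more than 80% power fits 50 completers (about 0.27/yr drop-out), not clearly the 0.36/yr listed as its input, which leaves about 44 completers and about 76–79% power

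*SAP*

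**What the plan says.** The Statistical power paragraph of the SAP opens: "with an n=75 and 50 completers, we will have >80% chance of detecting a difference in the rate of BMD AP lumbar spine increase" of 0.024 g/cm² per year, two-sided at 0.05. The figure came from random-slopes software, which handles drop-out by weighting the information for each follow-up time by its probability. The inputs are: "The variance of the intercept was 0.024, slope 0.000211, covariance 0.00199", residual variance 0.00092, and "an exponential drop-out rate of 0.36/yr, which is greater than we expect".

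Other statements bear on how this is read:

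- The end of the same paragraph, on the withdrawal period, assumes at least 43 patients at 18 months and says 50 are expected.
- The protocol (Research Design and Methods) says the team will try to replace drop-outs so that 50 complete, and that the study is powered for 50.
- The protocol (Follow-up visits) schedules "DXA scan (12 month, 18 month, and 24 month visits". Patients who leave after at least 9 months are asked to attend a final visit identical to month 18.
- The protocol (Baseline) repeats the DXA only when baseline falls more than 6 weeks after screening.
- The SAP (Data analysis plan) lets mean intercept and slope differ by treatment group and gender.

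**The concern.** The power claim carries two drop-out assumptions, and they give different numbers of completers. Fifty of 75 is the expected outcome. The listed rate of 0.36/yr is described as worse than expected. A reader will take the claim to hold even under that worse rate, so that the design has a cushion against attrition. If the printed power belongs to 50 completers instead, the cushion is not there. This is the power for the primary endpoint, and it supports the choice of 75 patients. The concern is whether the figure is matched to its stated input.

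**Working it through.** **Inputs.** From the SAP: intercept variance 0.024, slope variance 0.000211, covariance 0.00199, residual variance 0.00092, slope difference 0.024 g/cm²/y, two-sided 0.05, N = 75. From the protocol: DXA at 0, 1 and 1.5 years for an 18-month endpoint. Assumed: 1:1 allocation (37.5 per arm) and these three scan times in the software.

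**Step 1: completers.**

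- At 0.36/yr: 75 × exp(−0.36 × 1.5) = 75 × 0.5827 = 43.7.
- Rate that leaves 50 of 75: −ln(50/75)/1.5 = 0.4055/1.5 = 0.270/yr.

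**Step 2: method.** The information from one patient with scan times in Z is Z′(σ²I + ZΨZ′)⁻¹Z. It is averaged over three patterns: baseline only, baseline plus 12 months, and all three scans. The weights are the exponential drop-out probabilities. Then

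- Var(slope difference) = [I⁻¹]slope × (2/37.5)
- Power = Φ(0.024/SE − 1.96)
- Difference detectable with 80% power = (1.960 + 0.842) × SE

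**Step 3: the SAP's figure, with 50 completers (0.270/yr).** The pattern weights are 0.237, 0.096 and 0.667, and [I⁻¹]slope = 0.001375.

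- SE = √(0.001375 × 0.05333) = 0.00856
- Power = Φ(2.803 − 1.960) = Φ(0.843) = 80.0%
- Detectable difference = 0.0240, which matches the printed 0.024

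**Step 4: the listed rate, 0.36/yr.** The pattern weights are 0.302, 0.115 and 0.583, and [I⁻¹]slope = 0.001529.

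- SE = √(0.001529 × 0.05333) = 0.00903
- Power = Φ(2.658 − 1.960) = Φ(0.698) = 75.7%
- Detectable difference = 0.0253

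**Step 5: exit and repeat scans.** An exit DXA is placed at the time of leaving for everyone who leaves after 0.75 years. A repeat baseline DXA is treated as a second scan at time zero. The repeat shares, and the half attendance at exit visits, are assumptions; the documents give neither.

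| Drop-out | Exit DXA | Repeat baseline DXA | Power |
|---|---|---|---|
| 0.270/yr | none | none | 80.0% |
| 0.270/yr | all | none | 82.5% |
| 0.36/yr | none | none | 75.7% |
| 0.36/yr | all | none | 79.2% (detectable difference 0.0242) |
| 0.36/yr | all | 10% of patients | 80.7% |
| 0.36/yr | half | 20% of patients | 80.4% |
| 0.36/yr | none | 30% of patients | 80.0% |

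**Step 6: other choices at 0.36/yr.** Six-monthly DXA gives 79.1% (81.9% with all exit scans), but no 6-month DXA is scheduled. A t reference distribution in place of the normal gives 74–75%. Allocation of 2:1 gives 70.7%.

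**The case against.** The best defence is that the power sentence is explicitly conditional on 50 completers, and on that condition the calculation reproduces it at 80.0%, or 82.5% with full exit scans. The SAP itself separates the expected 50 from a pessimistic number near 43, and the protocol plans to try to replace drop-outs. At 0.36/yr with full exit scans, the detectable difference of 0.0242 rounds to the printed 0.024. A modest share of repeat baseline scans brings power back to 80%. The scan times and allocation entered in the software are not shown in the available text and may have differed from the current visit list.

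Most of this stands, and it limits the point. It does not remove it. The SAP names 0.36/yr as an input to the calculation, and replacement is a different assumption from 75 patients followed at that rate. Exit visits are requested, not assured. No statement in the available text says that the power figure counts exit or repeat scans.

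A reader might go further and infer that the trial is underpowered, that only the 0.27/yr reading can reach 80%, or that more patients must be enrolled. The documents do not support these readings. Several scan patterns the protocol allows reach about 80% at 0.36/yr, the target is 50 completers with replacement attempted, and the software's inputs cannot be checked here.

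**Conclusion.** The point holds in a limited form. The printed power agrees with 50 completers, where it is about 80% on scheduled scans and not clearly above it. At the listed 0.36/yr it is about 76% on scheduled scans and 79% with full exit scans, reaching about 80% or slightly more only with some repeat baseline scans as well. The claim of more than 80% therefore does not clearly survive the rate the SAP calls pessimistic. The shortfall is about 1 to 4 points, equivalent to a detectable difference of 0.0242 to 0.0253 instead of 0.024 g/cm²/y.

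The mismatch between 0.36/yr and 50 of 75 completers needs no modelling. The power figures rest on 1:1 allocation, DXA at 0, 12 and 18 months, arm-specific intercepts and slopes, and a normal reference. The statement should be corrected; the design is not called into question.

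**What to change.** State one drop-out assumption and one scan schedule for the power claim, and give the figure that goes with them. For example: with 75 enrolled and 50 completers (0.27/yr), about 80% power for 0.024 g/cm²/y; at 0.36/yr (about 44 completers), about 76–79%, or 80% power for about 0.025 g/cm²/y (0.0242 with full exit scans). Say which DXA times and allocation ratio were entered, and whether exit and repeat baseline scans are counted. If replacement of drop-outs is part of the assumption, say so there.

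The cost is a sentence or two in the SAP and a slightly less favourable stated figure. No patients or procedures are added, and the analysis model stays as specified.

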Skeletal Physiology Dysregulation in Obesity: The Role of Growth Hormone

NCT# 01724489

Version Date: November 7th, 2019

PARTNERS HUMAN RESEARCH COMMITTEE PROTOCOL SUMMARY

Answer all questions accurately and completely in order to provide the PHRC with the relevant information to assess the risk-benefit ratio for the study. Do not leave sections blank.

PRINCIPAL/OVERALL INVESTIGATOR [name]

PROTOCOL TITLE

Skeletal Physiology Dysregulation in Obesity: The Role of Growth Hormone

FUNDING

VERSION DATE 10.16.19

SPECIFIC AIMS

Concisely state the objectives of the study and the hypothesis being tested.

Specific Aim 1: Low-dose GH administration for 18 months to osteopenic obese men and women will increase bone mass, improve bone microarchitecture and increase bone strength.

We will investigate in osteopenic men and women with obesity and relative IGF-1 deficiency, whether GH administration for 18 months to increase IGF-1 levels within the normal range results in:

- A. Increased BMD
- B. Improved bone microarchitecture, including trabecular and cortical thickness.
 - The increase in trabecular thickness will be mediated primarily by GH and the effect on cortical thickness by IGF-1
- C. An increase in bone strength, as determined by finite element analysis

Specific Aim 2: We will investigate mechanisms responsible for the increase in bone strength due to GH administration. We hypothesize that the increase in strength will be mediated by:

- **A.** A reduction in bone marrow fat mediated by a decrease in Pref-1 associated with an increase in osteoblast activity, assessed by markers of bone formation, including P1NP
- B. Increased insulin, in associations with an increase in undercarboxylated osteocalcin
- **C.** Improved body composition, including a decrease in abdominal adiposity and lipid deposits in muscle and liver, and an increase in muscle mass
- D. A reduction in inflammatory cytokines and improvement in the serum lipoprotein apoB
- E. An increase in circulating vitamin D.

BACKGROUND AND SIGNIFICANCE

Provide a brief paragraph summarizing prior experience important for understanding the proposed study and procedures.

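### The SAP's SD for cortical thickness (0.0015 mm) and its detectable difference (0.012 mm/y) cannot both be right: the rule that reproduces trabecular thickness gives 0.0024 mm/y.

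*SAP*

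**What the plan says.** Cortical thickness is part of Specific Aim 1B in the Protocol: "Improved bone microarchitecture, including trabecular and cortical thickness". Bone microarchitecture is the first secondary endpoint listed for Aim 1 under the Protocol's study endpoints.

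The SAP (Statistical Power and Statistical Analysis) takes its variability figures for the two thickness measures from one source, "based on our preliminary data in obese men receiving placebo for 6 months". The SDs of change and the detectable increases stand together in the same sentence: "TbTh was 0.0047mm and of CoTh was 0.0015mm, we will be able to detect an annual increase of 0.008mm and 0.012mm, respectively". The SAP gives no separate sample size, power level or method for cortical thickness.

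Just before this, for the Aim 2 primary endpoint, the SAP states the standardised difference that the trial can detect: "with 50 completers we can detect 0.81 x SD of the difference in bone marrow fat content over a year".

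**The concern.** For a fixed sample size, power and significance level, the detectable difference is proportional to the SD. The two thickness measures share the preliminary sample, the 6-month period and the planned trial, so the measure with the smaller SD should have the smaller detectable difference. The SAP has it the other way round.

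What is at stake is the reading of a cortical thickness result, above all a null one. If the printed SD is right, the plan understates its own sensitivity about five-fold and no power is lost. If the true SD is larger, the stated 0.012 mm/y may be right, or it may lie well below 80% power. A reader cannot tell which case applies.

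**Working it through.** **Inputs.** From the SAP power section: SD of 6-month change 0.0047 mm (TbTh) and 0.0015 mm (CoTh); stated detectable increases 0.008 and 0.012 mm/y; 50 completers; a detectable difference of 0.81 SD for bone marrow fat. Assumed: 25 per arm, and 80% power at two-sided 0.05. The SAP states that power and level for neighbouring secondary endpoints but does not repeat them for this pair. Doubling a 6-month difference to an annual rate is inferred.

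**Step 1: reproduce the SAP's multiple.** A two-sample t test with 25 per arm, two-sided 0.05 and 80% power (noncentral t) needs d = 0.8087. This matches the stated 0.81.

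**Step 2: reproduce trabecular thickness.** Detectable annual difference = 2 × d × SD = 2 × 0.8087 × 0.0047 = 0.0076 mm/y. This rounds to the stated 0.008.

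**Step 3: apply the same rule to cortical thickness.** 2 × 0.8087 × 0.0015 = 0.00243 mm/y, against 0.012 stated. The ratio is 0.012 / 0.00243 = 4.9.

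**Step 4: a check that needs no power formula.** Divide each stated difference by its SD, letting every printed figure vary within its rounding.

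| Endpoint | As printed | Lowest | Highest |
|---|---|---|---|
| TbTh | 0.008 / 0.0047 = 1.70 | 0.0075 / 0.00475 = 1.58 | 0.0085 / 0.00465 = 1.83 |
| CoTh | 0.012 / 0.0015 = 8.0 | 0.0115 / 0.00155 = 7.42 | 0.0125 / 0.00145 = 8.62 |

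The ranges do not overlap. Allocation, power, significance level and annualisation multiply both endpoints by the same factor, so none of them can fit both.

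**Step 5: vary the assumptions.**

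| Variant (annual rate, t test) | TbTh, mm/y | CoTh, mm/y |
|---|---|---|
| 25/25, 80% power | 0.0076 | 0.0024 |
| 20/30, 80% power | 0.0078 | 0.0025 |
| 17/33, 80% power | 0.0080 | 0.0026 |
| 25/25, 90% power | 0.0088 | 0.0028 |

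Other variants (one-sided tests, 85% power, other arm sizes, other annualising factors) also left CoTh between 0.0007 and 0.0028 mm/y.

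**Step 6: work back from 0.012.** The SD it needs is 0.012 / (2 × 0.8087) = 0.0074 mm. Rounding of 0.012 gives 0.0115 / 1.6174 = 0.0071 to 0.0125 / 1.6174 = 0.0077 mm.

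**Step 7: consequences by true CoTh SD.** An increase of 0.012 mm/y is 0.006 mm over 6 months.

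| True 6-month SD | Detectable, mm/y | Power at 0.012 mm/y |
|---|---|---|
| 0.0015 mm (as printed) | 0.0024 | above 99.9% |
| 0.0074 mm (implied by 0.012) | 0.012 | 80% |
| 0.015 mm (assumption: decimal shift) | 0.024 | 28% |

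**The case against.** The strongest reply is that the rule is inferred. The SAP never writes down 0.81 times the 6-month SD times two. The doubling rests on TbTh alone, and the failure-load figure does not follow it (316 / 570 = 0.55 SD). This is true, but the comparison of ratios in step 4 does not depend on the rule.

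A random slopes model could give each endpoint its own multiplier, through the split between slope and residual variance. It cannot rescue the figure. A 6-month change SD of 0.0015 mm caps the slope SD at about 0.0015 / 0.5 = 0.003 mm/y, and 0.8087 × 0.003 = 0.0024 mm/y is then roughly the most that would be needed.

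The sentence also does not call 0.012 the smallest detectable increase. With an SD of 0.0015 mm the claim would be conservative rather than false. That stands for one of the three cases in step 7, but the TbTh figure beside it is an 80% power figure, and nothing tells the reader that the CoTh figure is of another kind.

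A one-digit slip is possible: an SD of 0.0075 mm gives 2 × 0.8087 × 0.0075 = 0.0121, which rounds to the stated 0.012. This is plausible but unproven, and the same look-up settles it. The 0.015 mm case has no support in the documents and only illustrates the range.

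Finally, this is one parameter within a secondary endpoint, and the trial is sized on BMD. That limits the importance of the point but does not remove the inconsistency.

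**Conclusion.** The concern holds. The stated CoTh difference does not follow from the stated CoTh SD: 0.012 against 0.0024 mm/y, a 4.9-fold gap. That the two pairs conflict rests only on the printed figures and on both endpoints sharing one design. The value 0.0024 also assumes 25 per arm, 80% power at two-sided 0.05 and doubling to a year. The documents do not show which CoTh figure is wrong, so the error may mean understated sensitivity, a correct 0.012 with a misprinted SD, or too little power at 0.012. It should be fixed because Aim 1B names the endpoint. Sample size, design, analysis and primary BMD power are unaffected.

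**What to change.** 1. Check the CoTh SD of 6-month change against the preliminary data.
2. Restate the SD and the detectable annual difference so that they agree under the rule used for TbTh, and write that rule down: allocation, power, significance level and the step from 6 months to a year.
3. Do not replace 0.012 with 0.0024 until the SD is confirmed.

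Two queries on the same paragraph can be settled alongside. Neither is a proven error, and the conclusion above does not rest on them.

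- *Failure load.* The SAP claims 80% power if the "true rate of difference in estimated failure load between the treatments is 316 units", with an SD of 570. State the time unit of the 316 and the period of the 570. At face value d = 316 / 570 = 0.554, power is 48%, and 0.8087 × 570 = 461 units would be detectable. If 316 is per year over 18 months and 570 is the SD of 18-month change, d = 316 × 1.5 / 570 = 0.832 and power is 82%.
- *Identical entries.* The SAP lists "vitamin D of 0.025 ng/ml, hsCRP of 0.025 mg/l, and apoB of 18.6 mg/dl per year". Check the two 0.025 values against the preliminary SDs for a copying or scale error.

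The cost is a look-up in the preliminary data and a change of SAP wording.

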Briefly describe study design and anticipated enrollment, i.e., number of subjects to be enrolled by researchers study-wide and by Partners researchers. Provide a brief summary of the eligibility criteria (for example, age range, gender, medical condition). Include any local site restrictions, for example, "Enrollment at Partners will be limited to adults although the sponsor's protocol is open to both children and adults."

Over the five years of this proposal, we expect to screen 300 patients in order to enroll 75 (38 healthy women and 37 healthy men) total men and women with obesity, osteopenia and relatively low IGF-1, adiposity for an evaluable 50 subjects. We will attempt to replace subjects who have dropped out of the study to ensure 50 completers at 18 months (for which the study is powered).

Eligibility:

Subjects will undergo a pre-study screening visit to determine eligibility for the study.

Inclusion criteria:

- Ages 18-65 and generally healthy
- $BMI \ge 25 \text{ kg/m}^2$

Partners Human Subjects Research Application Form Version Date: June 1, 2005

- BMD T or Z-score \leq -1.0 (as measured by DXA)
- IGF-I within or below the mean (plus 10% above the mean) for age and gender **Exclusion criteria**
- For women: amenorrhea for 3 months or more if premenopausal, pregnancy or breastfeeding, polycystic ovary syndrome
- Elevated creatinine or TSH levels; alanine amino transferase levels greater than 2 times the upper limit of normal
- History of diabetes mellitus, cancer or other serious chronic disease
- Use of osteoporosis medications
- Medication that could affect bone metabolism within the past three months, such as chronic oral glucocorticoids, gonadal steroids, or anticonvulsants
- Hct > 5 units below the lower limit of normal
- Routine MRI exclusion criteria including the presence of pacemaker or cerebral aneurysm clips
- Osteoporosis, that, according to WHO classification (BMD T score less than or equal to 2.5 at the AP spine, total hip or femoral neck), would warrant treatment consideration.

Briefly describe study procedures. Include any local site restrictions, for example, "Subjects enrolled at Partners will not participate in the pharmacokinetic portion of the study." Describe study endpoints.

Screening Visit: (n=300: 150 healthy obese women and 150 healthy obese men)

- A complete medical history, physical examination, height, weight, waist and hip circumferences. Calculation of BMI, waist:hip ratio.

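### The 80% power stated for bone strength (316 units at SD 570) does not follow from those figures with 50 completers; it needs an assumption about time scale or type of SD that the SAP does not state.

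*SAP*

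**What the plan says.** The SAP section Statistical Power and Statistical Analysis says that "for FEA we will have a power of 80% at a two-sided" 0.05 level, provided that the true difference rate in "estimated failure load between the treatments is 316 units, based on an assumption that the SD is 570 units". The SD of 570 is taken from a published external study. The clause gives no time unit for the 316, no sample size of its own and no skeletal site. It does not say whether 570 is the SD of a level, of a change or of a yearly rate.

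The sample size around the clause is 50 completers in total. The SAP's power paragraph opens "with an n=75 and 50 completers", and the Protocol (Research Design and Methods) plans replacement of drop-outs "to ensure 50 completers at 18 months (for which the study is powered". For the Aim 2 primary endpoint, the same SAP paragraph says that "with 50 completers we can detect 0.81 x SD of the difference in bone marrow fat content over a year".

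Bone strength is Specific Aim 1C in the Protocol ("An increase in bone strength, as determined by finite element analysis") and a secondary endpoint of Aim 1 under Study endpoints.

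**The concern.** Two detectable differences in one paragraph appear to rest on the same 50 completers, yet one is 0.81 SD and the other 0.554 SD. A two-group comparison has only one 80% detectable multiple for a given sample size and alpha. Either the FEA figures are on different scales that the text does not name, or the stated power is wrong.

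Bone strength is also the outcome that the Aim 2 hypotheses seek to explain. If 316 and 570 are on the same scale, a true effect of 316 units would be missed about half the time, while a null result would be read as coming from a test with 80% power.

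**Working it through.** **Inputs.** From the SAP power paragraph: difference 316, SD 570, two-sided alpha 0.05, power 80%, 50 completers. Assumption: 1:1 allocation, so 25 per arm; the supplied text does not give the ratio. All t-test results use the noncentral t distribution.

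**Step 1: reproduce the plan's marrow-fat multiple.** With 25 per arm and 80% power, the detectable difference is 0.809 SD by the t-test. By the normal approximation it is (1.960 + 0.842) x sqrt(2/25) = 0.792 SD. The SAP's 0.81 reproduces, which supports both the method and the 1:1 assumption.

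**Step 2: apply the same method to FEA at face value.**
- Standardised difference: 316/570 = 0.554.
- Power at 25 per arm: 48.4% (t) or 50.0% (normal).
- Detectable difference at 80% power: 0.8087 x 570 = 461 units (t) or 452 units (normal).
- Completers needed for 80% power at 316 units: 52.05 per arm by t, so 53, or about 106 in total against the planned 50.

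**Step 3: where 316 may come from.** The standard error is 570 x sqrt(2/25) = 161.2, and 1.96 x 161.2 = 316.0. The stated difference therefore equals the critical value for significance with the power term (0.842 standard errors) left out. By the normal approximation that is the difference with 50% power. The match suggests an omitted term; it does not prove one.

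**Step 4: readings that might restore 80%.**

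| Reading | Power at the stated 316 | Comment |
|---|---|---|
| 316 per year, 570 the SD of an 18-month change: 316 x 1.5 = 474, and 474/570 = 0.832 SD | 82.1% (t) | Neither scale is stated. Detectable rate 461/1.5 = 307 per year |
| 570 an SD of levels, change scores analysed: change SD = 570 x sqrt(2(1 - r)) | 27% at r = 0, 48% at r = 0.5, 79% at r = 0.76, 81% at r = 0.77, 86% at r = 0.8 | r is not given |
| 570 an SD of levels, baseline-adjusted: SD = 570 x sqrt(1 - r²) | 80% at r = 0.73 | r is not given |
| 50 completers per arm | 78.4% (t) | Contradicts 50 completers in total |
| All 75 enrolled, 37.5 per arm | 65.9% (t) | Does not reach 80% |

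**Step 5: do the neighbouring thickness figures settle it?** The SAP gives SDs of 6-month changes. Doubled to a yearly scale, trabecular thickness gives 0.81 x 0.0047 x 2 = 0.0076 mm, close to the stated 0.008. Cortical thickness gives 0.81 x 0.0015 x 2 = 0.0024 mm, against the stated 0.012. One fits and one does not, so 0.81 SD is not a rule that the whole paragraph follows. The finding rests on the direct calculation in Step 2; marrow fat is corroboration.

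**The case against.** The yearly reading has real support in the text. The FEA clause speaks of a rate, neighbouring endpoints are given per year, and the planned analysis models slopes. On that reading 82% meets the claim. The gap between 307 and 316 per year is about 3% and does not count against it: the detectable rate is 317 with 47 completers, and 330 with the 43.7 implied by the SAP's drop-out rate (75 x exp(-0.36 x 1.5)). Nor does it conflict with the thickness figures. Doubling a 6-month change and dividing an 18-month change by 1.5 are the same operation, a change divided by its duration.

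The other reading has force too. If 570 describes levels between subjects, 48% does not follow for an analysis of change. The SAP's BMD variance components imply a correlation between baseline and 18 months of 0.026985/sqrt(0.02492 x 0.03136) = 0.965. If failure load behaved like BMD, which is an assumption, power at 316 units would be close to 100%.

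These points stand, and they rule out a stronger inference that a reader might draw: that the trial has only 48% power for bone strength. The documents do not support it, because they do not say what 570 measures or over what period 316 accrues. What the objection does not do is verify the sentence. Each reading that delivers 80% adds something the SAP leaves out, and the two call for different corrections.

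**Conclusion.** The concern holds in a conditional form. The inputs as printed do not give the power as printed: at face value on one scale, 50 completers give about 48% (t) to 50% (normal), and 80% needs about 461 units. This rests on 1:1 allocation and on 316 and 570 sharing a scale. The stated 80% is roughly right if 316 is per year and 570 is an 18-month change SD, or if 570 is an SD of levels with a high enough correlation (about 0.77 for change scores, 0.73 with baseline adjustment).

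A reader might also infer from the match with 1.96 standard errors that the authors certainly dropped the power term. That remains an inference.

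The consequence is limited. Failure load is a secondary endpoint, the sample size is justified on BMD, and the SAP states mediation power separately in terms of BMD. The sentence should still be corrected, because it cannot be verified and its most direct reading is wrong.

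**What to change.** Recompute and restate the FEA sentence, giving the time unit of the difference, what the SD of 570 measures (level or change, and over what period), the site (radius or tibia; the Protocol scans both) and the number per arm. Which figure to write depends on what the cited SD proves to be:

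- **SD of the change on the same scale as the difference:** 461 units at 80% power, with power of about 48% at 316 units.
- **316 a yearly rate and 570 the SD of an 18-month change:** 307 units per year at 80% power (461 over 18 months).
- **SD of levels:** the assumed baseline to follow-up correlation, its source and the resulting detectable difference.

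The 48% should not go into the SAP unless the first case is confirmed. The cost is one sentence and a check of the cited source. No patients are added and no analysis changes. The downside is that a stated figure may become less favourable.
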